Secondary 
 To evaluate the PK profile of single (fasted and fed) and repeat doses of GSK3494245 in healthy participants To examine dose proportionality following single 	
 SAD part: Derived PK parameters for GSK3494245 following single dose (fasted and fed) including area under the plasma drug concentration versus time curve (AUC(0-t), AUC(0-∞)), maximum observed plasma drug concentration (C_{max}), time to maximum observed plasma drug concentration (T_{max}), and apparent terminal half-life (t_{1/2}) as data allow. MAD part: as appropriate: 
 Day 1 AUC(0-t), AUC(0-∞), AUC(0-tau), C_{max}, T_{max}, t_{1/2}

Objectives	Endpoints

doses of GSK3494245
 
 To assess accumulation and time-invariance ratios of GSK3494245 To assess steady state following repeat doses of GSK3494245 	
 Day 4-7 morning trough plasma concentration (C_{tau}), Day 7 AUC(0-t), AUC(0-tau), C_{max}, T_{max}, t_{1/2}, CL_{ss} Additionally for TID regimen if conducted) : Day 6 evening dose AUC(0-t), AUC(0-tau), C_{max}, T_{max}, 
 Dose-proportionality assessment using derived PK parameters, as data allow: 
 SAD part: AUC(0-∞), C_{max} MAD part: Accumulation ratios assessment*, where data allow: RAUC(0-tau), RC_{max}, RC_{tau}. Time-invariance ratio calculation as AUC(0-tau on Day 7 to AUC(0-∞) on Day 1. Additionally for TID regimen if conducted: Time-invariance ratio calculation for TID regimen as AUC(0-tau) on Day 6 evening dose to AUC(0-∞) on Day 1 Steady state assessment for MAD part: C_{tau}

CCI

* Accumulation ratios calculated as the ratio of last dose to first dose PK parameters: RAUC(0-tau) = AUC(0-tau) on last dose (with the exception of TID for which the evening dose on Day 6 will be used) to AUC(0-tau) on first dose, RC_{max} = C_{max} on last dose to C_{max} on first dose, RC_{tau} = C_{tau} on last dose to C_{tau} on first dose.

Overall Design: This study will be a randomized, double-blind, placebo-controlled, 2-part study of the oral administration of GSK3494245 in healthy participants. As this will be the first time GSK3494245 is administered to humans, the study design may change based on emerging data as the study progresses.

This study is planned to include approximately 80 participants:

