4.1.4. Multiple Ascending Dose (MAD)

Prior to initiation of the MAD part, a review of all available safety, tolerability and PK data from the SAD part will be conducted. A formal interim analysis is not planned.

[figure not shown]
MAD consists of 5 cohorts (Cohorts 4, 5, 6, 7 and 8), each including 8 participants. Participants in each cohort will be randomised to receive repeat doses in the fed state of either GSK3494245 or placebo (blinded), administered in a 3:1 ratio according to the randomization schedule.

GSK3494245 or placebo will be administered BID for 7 days using a 12 h dosing interval, with only one dose administered on Day 7. Based on emerging data, the dosing regimen

may be altered to a three-times daily (TID) regimen, with doses administered 6 hours apart on each day

Up to a maximum of 5 dose levels will be studied in the MAD part as illustrated below:

Figure 2 Study Design (MAD part)

A = active drug; BID = twice-daily; TID = three-times daily; DL = dose level; P = placebo. Day 7 is morning dose only.

Note: For each new dose level the first two subjects in each cohort will act as sentinels.

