	
Dose Proportionality (SAD part)
 
Dose proportionality will be assessed following single doses of GSK3494245 for fasted and fed cohorts separately(SAD part) via analyses of AUC(0-∞) and C_{max}.
 
A statistical analysis will be performed using the power model. The analysis will be performed on log_e-transformed data. For each of these parameters a mixed effects model will be fitted with log_e (dose) as a fixed effect and individual participant fitted as random effects. Estimates of the mean slopes of log_e (dose) will be reported along with corresponding 90% confidence intervals (slope\approx1 implies dose proportionality).
 
Accumulation (MAD part)
 
The extent of accumulation of GSK3494245 will be based on AUC (RAUC_(0-tau)), C_{max} (RC_{max}) and Ctau (RCtau).
 
The focus of the statistical analysis will be to estimate the accumulation ratio, Ro, on the pharmacokinetics of GSK3494245. Following log_e-transformation, AUC(0-tau) on Day 1 and AUC(0-tau) on the day of last dose will be analysed by a mixed effect model, fitting fixed effect terms for dose, day, and day by dose interaction, and fitting subject as a random effect.
 
For each dose, point estimates and 90% confidence intervals for the differences “Day 7 - Day 1” (for BID) or “Day 6 evening dose – Day 1 morning dose” (for TID) will be constructed using the appropriate error term. The point estimates and associated 90% confidence intervals will then be exponentially back-transformed to provide point and 90% confidence interval estimates for the ratios “Day 7: Day 1” (for BID) or “Day 6- Day 1” (for TID) for each active dose. If both the dose and day by dose interaction terms are not significant, a single point estimate and confidence interval pooled across all doses will also be constructed.
 
RC_{max} and RCtau will be estimated in a similar approach.
 
Steady State analysis (MAD part)
 
Steady state will be assessed following repeat dose of GSK3494245 (MAD part) via analyses of trough plasma concentration (Ctau)
 
A statistical analysis will be performed using mixed effect model on log_e transformed endpoint. A mixed effects model will be fitted with log_e (dose) as a fixed effect and subject fitted as random effect. The coefficients of the slopes for the day effect on log scale for each dose, along with corresponding 90% confidence intervals, will be used to determine whether steady state was achieved.

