Study intervention Assignment	
This study is planned to include approximately 80 participants (excluding additional up to 16 subjects from the 2 optional cohorts)
 
Dose Escalation (SAD): Cohort 1, 2 and 3a will each have 6 participants in active versus 2 participants in placebo (i.e., in a 3:1 ratio) at each dose level.
 
Food Effect: Cohort 3 will contain up to 16 participants in a 1:1 ratio for (fed and fasted) versus (fasted and fed) for the selected dose of GSK3494245 and placebo.
 
MAD Part:
 
 • MAD Part consists of up to 40 participants in up to 5 cohorts (excluding possible replacements): 
 • Each of cohort (4,5,6,7 and 8) will have 6 participants in active versus 2 participants will receive placebo (i.e., in 3:1 ratio) at each repeat dose level.
Interim Analysis	No interim analyses are planned for this study.

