AUC (0-∞)	Area under the concentration-time curve extrapolated to infinity will be calculated as: $AUC(0 - \infty) = AUC(0 - t) + \frac{C(t)}{\lambda_z}$ 
(NOTE: λ_z is the terminal phase rate constant and C(t) is the last quantifiable concentration. % of the extrapolated area should not exceed 20%. Any value of AUC (0-∞) derived with more than 20% extrapolation should be flagged and excluded from summary statistics if >30%).

AUC(0-∞)_D	Area under the concentration-time curve extrapolated to infinity normalized by dose will be calculated as: $AUC(0-\infty)_D = AUC(0-\infty)/D$
R ₂ adjusted*	The goodness of fit statistic for the terminal elimination phase, adjusted for the number of points used in the estimation of λ_z .
λ_z	λ_z is the terminal phase rate constant. A minimum number of three data points in the terminal phase will be used starting at any post-C _{max} data point. The adjusted correlation coefficient (R ₂ adjusted) in general should be greater than 0.90. Any value < 0.90 but ≥ 0.8 will be flagged but may be used at the PK Scientist's best knowledge and judgment, any value < 0.8 should be considered for exclusion from the statistical analysis. All the derived parameters that include λ_z in their calculation (i.e., t _{1/2} , AUC (0-∞)) will need to be flagged or excluded from statistical analysis accordingly. The interval used to determine λ_z should be equal or greater than 1.5-fold the estimated half-life or otherwise flagged and used at the PK Scientist's best knowledge and judgment.
λ_z upper limit*	The upper limit on time for values to be included in the calculation of λ_z .
λ_z lower limit*	The lower limit on time for values to be included in the calculation of λ_z .

Parameter	Parameter Description
λ_z number of points*	The number of time points used in computing λ_z .
% AUCex*	Percent of AUC_{∞} that is extrapolated beyond last quantified concentration
CL/F*	The apparent clearance will be calculated as Dose/AUC (0- ∞)
RAUC(0-tau), RCmax, RCtau	
Accumulation ratio, calculated from comparison of single dose and multiple dose administration data:
 $RCmax = \text{Day 7 } Cmax / \text{Day 1 } Cmax$ $RCtau = \text{Day 7 } Ctau / \text{Day 1 } Ctau$ 
Where for RCtau Concentration at the end of the morning dose time interval will be taken

NOTES: *Additional exploratory parameters have been included which will be listed only.

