7.4.2. Main analytical approach

Statistical analysis will be to estimate the accumulation ratio, R_o , on the pharmacokinetics of GSK3494245. Following \log_e -transformation, AUC(0-tau) on Day 1 and AUC(0-tau) on the day of last dose will be analyzed by a mixed effect model.

- Fixed effect: dose, day, and dose*day
- Random effect: Subject
- Data from all available doses will be considered. An unstructured covariance structure will be considered for the G matrix describing the between subject variability.
- The Kenward and Roger method for approximating the denominator degrees of freedom and correcting for bias in the estimated variance-covariance of the fixed effects will be used.
- Distributional assumptions underlying the model used for analysis will be examined by obtaining a normal probability plot of the residuals and a plot of the residuals versus the fitted values (i.e., checking the normality assumption and constant variance assumption of the model respectively) to gain confidence that the model assumptions are reasonable.
- If there are any departures from the distributional assumptions, alternative transformations such as data squared or square root of data, will be explored.
- If this model fails to converge, alternative covariance structures may be considered in the following order (1) Compound Symmetry (CS) and (2) Variance Components (VC) (3) First order autoregressive.

Model Results:

- For each dose, point estimates and 90% confidence intervals for the differences “Day 7 - Day 1” (for BID) or “Day 6 evening dose - Day 1 morning dose” (for TID) will be constructed using the appropriate error term.
- The geometric mean ratio and 90% CI for the ratios “Day 7: Day 1” (for BID) or “Day 6- Day 1” (for TID) after back transformation for each active dose.
- If both the dose and day by dose interaction terms are not significant, a single point estimate and confidence interval pooled across all doses will also be constructed.

Note: RCmax and RCtau will be estimated in a similar approach

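### The pooled accumulation ratio is conditional on a non-significant dose main effect, which does not bear on whether the ratio is constant across doses and will almost always be significant

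*SAP*

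**What the plan says.** SAP 7.4.2 log-transforms the exposure measure and states that "AUC(0-tau) on Day 1 and AUC(0-tau) on the day of last dose will be analyzed by a mixed effect model", with the terms "Fixed effect: dose, day, and dose*day" and participant as a random effect. RCmax and RCtau are to be handled in a similar way. A ratio to Day 1 with a 90% CI is always given for each dose. A pooled ratio is added only on this condition: "If both the dose and day by dose interaction terms are not significant, a single point estimate and confidence interval pooled across all doses". Protocol 9.5.2 sets the same condition ("If both the dose and day by dose interaction terms are not significant"), so it is not a slip in copying to the SAP. Neither document gives a significance level for these two tests.

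The response is not divided by dose. SAP Table 1 defines dose-normalised Cmax, AUC(0-t) and AUC(0-∞), but no dose-normalised AUC(0-tau) or Ctau, and 7.4.2 asks for none.

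On size, protocol 4.1.4 says "Up to a maximum of 5 dose levels will be studied in the MAD part", and SAP 1.2 says each cohort "will have 6 participants in active versus 2 participants will receive placebo".

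For TID, SAP 7.4.2 and Secondary Estimand 3 in SAP 1.1.2 compare the Day 6 evening dose with Day 1. SAP Table 1 defines RCmax and RCtau as Day 7 over Day 1 without regard to regimen, and for RCtau says "Concentration at the end of the morning dose time interval will be taken". The synopsis footnote carries the words "with the exception of TID for which the evening dose on Day 6 will be used" inside the RAUC definition only. The footnote in protocol section 3 has no exception.

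**The concern.** In this model the dose main effect asks whether mean log exposure, averaged over the two days, differs between doses. In an ascending-dose study it is expected to differ by design. Whether the ratio of last to first exposure differs between doses is a separate question, and only the day-by-dose term answers it. A condition that needs both terms to be non-significant therefore withholds pooling for a reason unrelated to whether pooling is valid.

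At stake is a planned output for a named secondary objective. Each dose has 6 active participants, so each per-dose ratio is fairly imprecise, and the pooled ratio is where the design gains precision.

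The rule also runs the wrong way: the condition is easiest to meet when few or closely spaced doses have been studied, which is when there is least information on whether accumulation depends on dose.

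**Working it through.** **Inputs.** Table 6 means for 30, 60, 120, 180 and 240 mg BID: AUC0-24 of 1819, 3828, 8057, 12450, 16955 ng·h/mL (9.3-fold) and Cmax of 464.1, 862.4, 1603, 2303, 2978 ng/mL (6.4-fold). Six active per dose. Between-participant CV (CVb) 30%, with 40% as the upper sensitivity value (protocol 9.2 and 9.3). Within-participant CV (CVw) 20% for AUC and 30% for Cmax, stated for Cohort 3 and assumed to carry over. Test level assumed 0.05; at 0.10 every probability below is smaller.

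**The plan's own figure.** With SD = √ln(1+CV²), the half-width is t(0.975, n−1)·SD/√n. At CVb 30% and n = 6, SD = 0.294 and the half-width is 0.308; exp(0.308)−1 = 36%, as stated. All nine rows of protocol Table 10 (SAP Table 2) reproduce to within 0.5 percentage points.

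**Dose term.** Dose varies between participants. A participant's mean over the two days has variance SDb² + SDw²/2. The test is F on k−1 and k(n−1) df, with noncentrality λ = n·Σ(ln mean − average)²/variance.

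- AUC, five doses, CVb 40%: variance = 0.1484 + 0.0392/2 = 0.168; sum of squares 3.29; λ = 6 × 3.29/0.168 = 117.5; critical F(4,25) = 2.76; probability of non-significance 2e-12.
- Cmax, three lowest doses, CVb 40%: variance = 0.1484 + 0.0862/2 = 0.1915; sum of squares 0.768; λ = 24.1; critical F(2,15) = 3.68; probability 1.7%.

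Probability that the dose term is non-significant, at CVb 30% / 40%:

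| Lowest doses studied | AUC (CVw 20%) | Cmax (CVw 30%) |
|---|---|---|
| 2 | 5.5% / 19% | 23% / 40% |
| 3 | 1e-6 / 4.5e-4 | 0.12% / 1.7% |
| 4 | 2e-13 / 7e-8 | 5e-7 / 1.6e-4 |
| 5 | <1e-15 / 2e-12 | 5e-11 / 6e-7 |

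The ratios of 95th percentile to mean in Table 6 imply, if log-normal, a CVb of 42-46% for AUC and 48-54% for Cmax. At 50%, Cmax gives 7% with three doses and about 9e-5 with five.

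**Joint rule.** In 20,000 simulated trials with five doses and a constant true ratio, both terms were non-significant in none for AUC (CVb 30-60%), in none for Cmax at CVb 30-40%, and in 0.16% for Cmax at 60%. The interaction alone was non-significant in about 95%.

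**Precision lost.** The 90% half-width is t·SDw·√(2/n).

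- CVw 20%: one dose, 1.708 × 0.198 × √(2/6) = 0.195, limits 0.82 to 1.22; five doses pooled, 1.699 × 0.198 × √(2/30) = 0.087, limits 0.92 to 1.09.
- CVw 30%: 0.75 to 1.34 for one dose; 0.88 to 1.14 pooled.

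On the log scale the pooled interval is narrower by about √5 = 2.24.

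**TID comparator.** Doses are 6 h apart, so the Day 7 morning dose follows a 12 h gap and the Day 6 evening dose a 6 h gap. Superposition used Table 3: KA 0.7/h, elimination rate CL/V = 3.81 × 0.06/1.28 = 0.179/h (scenario 1) or 6.67 × 0.06/1.28 = 0.313/h (scenario 2). RCmax is 1.68 from the Day 6 evening dose against 1.24 from Day 7 in scenario 1, and 1.33 against 1.05 in scenario 2. RCtau is 1.50 against 1.18, and 1.19 against 1.03.

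**The case against.** **The consequence is limited.** This stands. Per-dose ratios with 90% CIs are always produced, the pooled ratio is an additional output, no hypothesis is tested, and neither dose escalation nor the PK stopping criteria use it. At CVw 20% a per-dose interval of 0.82 to 1.22 is usable.

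**The condition is not impossible to meet.** A reader might infer that the pooled ratio can never appear, or that the AUC probabilities apply equally to Cmax and Ctau. The documents do not support that. Cmax probabilities are larger, and the number of cohorts is a maximum, so the part could stop after two dose levels. There is no Ctau prediction at all. If its spread over five doses resembled that of AUC or Cmax, even a CVb of 100% would give only about 2% to 10%.

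**Pooling has a cost.** The regimen may change from BID to TID, and ratios over 12 h and 6 h intervals are different quantities. Protocol 4.5.1 also reports saturable hepatocyte clearance, so a dose-dependent ratio is plausible; with 6 per dose the interaction test may miss it. Both points stand and limit the fix.

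**TID.** A reader might infer that the plan definitely takes RAUC from Day 6 and RCmax and RCtau from Day 7. It does not: SAP 7.4.2 extends its approach to all three, and the estimand groups them. What remains is a conflict with SAP Table 1 and the two protocol footnotes.

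**Conclusion.** The pooling condition tests the wrong quantity and should be changed. This follows from the model as written and needs no assumption on variability. That the condition will almost never be met does rest on assumptions: Table 6 means, CVb 30-40%, a 0.05 level, and about three or more doses spread over the planned range. On that basis the probability is at most 0.05% for AUC and 1.7% for Cmax, and far lower with four or five doses. If only the two lowest doses are studied it rises to 5-19% and 23-40%, because the test has little power and not because pooling is better justified. The loss is precision on a secondary summary: the upper limit is about +22% instead of +9% at CVw 20%, or +34% instead of +14% at CVw 30%, taking five doses pooled. Safety conclusions are unaffected.

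The TID comparator is a separate, conditional point of wording, but one that can change the reported RCmax materially.

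**What to change.** In SAP 7.4.2 and protocol 9.5.2, delete the dose main effect from the pooling condition. Within a single regimen, report the pooled ratio beside the per-dose ratios, and use the day-by-dose term, at a stated significance level, to comment on heterogeneity. Do not pool BID and TID cohorts together. Keep the per-dose ratios next to the pooled one, because a pooled value can mask a ratio that changes with dose.

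Separately, if TID is used, reconcile SAP 7.4.2 (including its reference to the day of last dose), SAP 1.1.2, SAP Table 1 and the accumulation footnotes in the protocol synopsis and section 3, so that RAUC, RCmax and RCtau all use one comparator dose. SAP 7.4.2 and the estimand already name the Day 6 evening dose, so aligning the rest to it is the smaller edit.

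The cost is wording in two documents and one added line of output per parameter and regimen. No extra sampling is needed: the TID schedule already has serial samples after both the Day 6 evening and the Day 7 dose.

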7.4.2.1. Intercurrent events and handling of missing data

The intercurrent events mentioned in Section 1.1.2. along with the corresponding strategies will be considered during this analysis.

- For treatment discontinuation due to any reason:

Subjects' data available up to the withdrawal will be included in the analysis where treatment discontinuation had not occurred. If a subject withdraws consent during a period, the missing data post withdrawal will not be imputed.

- For Subject use concomitant/prohibited medication:
The subject data post consumption of concomitant/prohibited medications (intercurrent event) will be analyzed as collected.

If multiple intercurrent events are observed, then the data will be handled using more than one strategy as described in Section 1.1.2. and interpretations of the results will be made accordingly.

Graphical presentations will be provided, if appropriate. All data will be listed. Details of the planned displays are provided in the Output Programming Specification (OPS) document. Data Displays will be based on GSK Data Standards and statistical principles.

7.5. Statistical analysis for Time Invariance (MAD part)

7.5.1. Endpoints/Variables

- The statistical analysis will be based on the ratio of AUC(0-tau) (i.e., AUC (0-12) for dosing is BID) on day 7 to AUC (0-∞) on day 1. If TID regimen is conducted, statistical analysis will be based on the ratio of AUC(0-tau) on Day 6 evening dose to AUC (0-∞) on Day 1.

Main analytical approach

A statistical analysis will be performed using mixed effect model on log_e transformed endpoint.

- Fixed effect: Day
 - Random effect: Subject
-
- Data from all available doses will be considered. An unstructured covariance structure will be considered for the G matrix describing the between subject variability.
 - The Kenward and Roger method for approximating the denominator degrees of freedom and correcting for bias in the estimated variance-covariance of the fixed effects will be used.
 - Distributional assumptions underlying the model used for analysis will be examined by obtaining a normal probability plot of the residuals and a plot of the residuals versus the fitted values (i.e., checking the normality assumption and constant variance assumption of the model respectively) to gain confidence that the model assumptions are reasonable.
 - If there are any departures from the distributional assumptions, alternative transformations such as data squared or square root of data, will be explored.

- If this model fails to converge, alternative covariance structures may be considered in the following order (1) Compound Symmetry (CS) and (2) Variance Components (VC) (3) First order autoregressive.

Model Results:

- The summary measure will be the point estimate and 90% CIs of mean difference of 'AUC(0-tau) at Day 7– AUC (0-∞) at Day 1' based on the log-transformed data and after back-transformation of this estimated difference, the geometric mean of the ratio 'AUC (0- tau) at Day 7: AUC(0-∞) at Day 1' and 90 % CI of ratio will also be presented for each active dose.

7.5.1.1. Intercurrent events and handling of missing data

The intercurrent events mentioned in Section 1.1.2. along with the corresponding strategies will be considered during this analysis.

- For treatment discontinuation due to any reason:

Subjects' data available up to the withdrawal will be included in the analysis where treatment discontinuation had not occurred. If a subject withdraws consent during a period, the missing data post withdrawal will not be imputed.

- For Subject use concomitant/prohibited medication:

The subject data post consumption of concomitant/prohibited medications (intercurrent event) will be analyzed as collected.

If multiple intercurrent events are observed, then the data will be handled using more than one strategy as described in Section 1.1.2. and interpretations of the results will be made accordingly.

Graphical presentations will be provided, if appropriate. All data will be listed. Details of the planned displays are provided in the Output Programming Specification (OPS) document. Data Displays will be based on GSK Data Standards and statistical principles.

